14.5.2 Turnaround Time

Time from swab collection to result availability will be recorded in minutes for both the new POCT and the established test. As both tests are conducted on the same participant, paired comparisons will be analysed using the paired t-test (or Wilcoxon's if data are non-normally distributed). Mean (or median) differences will be reported with 95% confidence intervals and p-values.

14.5.3 Patient Acceptability

Participants will complete a brief questionnaire assessing the acceptability of the new POCT including comfort and willingness to repeat the test. Responses will be collected using Likert scales and categorical items. Data will be analysed using descriptive statistics and comparisons with the standard test will be conducted using Wilcoxon's signed-Rank test using JASP software.

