5.0 PROTOCOL SYNOPSIS

C4d C	
Study Summary	
Protocol Title	Evaluation of Digital Microfluidic Molecular Point Of Care Testing for Respiratory Pathogens Diagnosis
Short Title	Study for Multiplex Assessment and Respiratory Test evaluation; SMART
Study Objectives	To evaluate the analytical performance, turnaround time, operability and acceptability of a novel multiplex respiratory pathogens point of care test device compared to currently available point of care testing.
Study Procedures	Participants will be swabbed to provide samples which will be analysed by standard testing and by the novel multiplex device. The procedures will take place in a single visit in the Emergency Department at Addenbrooke's Hospital in Cambridge. Additional relevant data will be collected from the participants' hospital medical records. No further participant involvement is required.
Study Sponsor	Logilet (UK) Ltd
Sponsor	[name] ([name])
Representative	Product Manager
Study Design	This is a prospective, single centre, single visit, diagnostic performance study. There is no therapeutic agent involved and therefore no randomisation into treatment arms. Two nasopharyngeal swabs will be taken simultaneously from each participant (one from either nostril) and used for Point Of Care Testing using the current gold standard and novel in vitro diagnostic devices. In this way, participants will act as their own controls for comparison of results. If the initial standard test is negative but the participant continues to exhibit clinical symptoms of respiratory infection, a further swab may be taken and tested as per Cambridge University Hospitals NHS Foundation Trust (CUH) policy with another standard device.
Investigational Medical Device	The Logicore System in vitro diagnostic device utilises digital microfluidics to rapidly test for the presence of 6 respiratory pathogens, namely SARS-CoV-2, Influenza A (FluA), Influenza

	Ţ
	B (FluB), Respiratory Syncytial Virus (RSV), Mycoplasma pneumoniae (MP) and human adenovirus (HAdV). The Logicore System produces results in approximately 63 minutes and is expected to feature improved sensitivity when compared to the current gold standard testing device.
Study Location	Cambridge University Hospitals NHS Foundation Trust (CUH)
	Emergency Department
	Addenbrooke's Hospital Cambridge Biomedical Campus
	[name]
	Cambridge
	[name]
Study Duration	When the sample size has been reached, or a maximum of four

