11.0 STUDY DESIGN

This is a prospective, single-centre, diagnostic accuracy study, being conducted at Addenbrooke's Hospital in Cambridge. Participants can be any age but must exhibit acute respiratory symptoms on presentation at the Emergency Department and require standard of care diagnostic testing as per CUH Trust IPC policy.

The study will be performed in accordance with the Declaration of Helsinki⁵, principles of Good Clinical Practice⁶ and local and regulatory requirements.

The study is aiming to recruit 400 participants. There is no Investigational Medicinal Product involved and therefore no treatment arms and no randomisation. Swab samples taken from each participant will be tested by standard POCT (control data) and by Logicore System POCT device.

Members of the research ream will utilise Personal Protective Equipment (PPE) in line with the CUH Infection Prevention and Control Guideline.

There is only one visit required for each participant, during which the following data will be collected:

- Study identifying number
- Date of Visit and Study Assessments (presentation at ED)
- Sex
- Age in years
- Emergency Care Data Set (ECDS) presentation code
- Clinical signs and symptoms of respiratory tract infection
- Date of onset of clinical symptoms of respiratory tract infection
- Time nasopharyngeal swabs taken
- Time results available from Cepheid and Logicore System devices (to establish turnaround time in minutes)
- Hospital admission required? Y/N
- Intensive care admission required? Y/N
- NEWS-2 Score for participants 15 years of age and above
- PEWS (Paediatric Early Warning Score) for participants less than 15 years of age
- Arrival by ambulance? Y/N
- Respiratory rate (breaths per minute)
- Temperature (in °C)
- Heart rate (beats per minute)
- Blood pressure (systolic and diastolic)
- Oxygen saturation (%)
- Confirmation that Logicore System Instructions For Use (IFU) were followed to test the sample using the new device
- Participant and staff assessment of acceptability
- Adverse event details.

Following discharge from the ED (to home, nursing home or a hospital ward etc), the following additional information will be collected:

- 7, 14 and 30-day mortality
- Discharge diagnosis confirmation.

To assess the acceptability of the testing process, each participant will be asked the following question:

'How unpleasant was the swab'?

The participants must rate the swabbing process according to the following categories:

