- 1) Very unpleasant
- 2) Slightly unpleasant

- 3) I didn't mind
- 4) I really didn't mind.

Thus, the greater the aggregated score for all participants, the more acceptable the swab process was felt to be.

Each participant will also be asked a second question as follows:

'If you had to have the swab done again, how would you feel about it'?

The participants must give an answer from the following responses:

- 1) Happy
- 2) I wouldn't mind
- 3) Unhappy.

To assess the acceptability of using the Logicore System, ED research team staff will be asked the following question:

'How difficult was the Logicore System to use'?

The staff must rate the Logicore System process according to the following categories:

[figure not shown]
- 1) Very difficult
- 2) Slightly difficult
- 3) Quite easy
- 4) Very easy.

Thus, the greater the aggregated score for all staff, the more acceptable the Logicore System was felt to be.

The study duration will be a one-off face-to-face visit for participants. The Research Nurse or designated member of the ED research team will use the hospital electronic patient record system to obtain the required post-discharge details. Participants will be considered as in the study from the date of signed informed consent form until the date of discharge from the ED. As there is no additional hospital visit required for the study, there is no provision for participant's travel or sustenance expenses, and participants will not be paid to take part in the study.

Figure 1: Sample Collection and Testing Process

If Cepheid and Logicore System results are both positive for the same pathogen, or both negative for all pathogens then the results will simply be recorded.

A. If the Cepheid result is positive but the Logicore System result is negative, the Logicore System test will be classed as a false negative.

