13.5 Schedule of Events

13.5.1 Per Participant Activities

Activity	At ED Visit
Review of PIS and signing of ICF/Assent form	Х
Signs and symptoms of acute respiratory tract infection	Х
Temperature	Х
Heart rate, respiratory rate, blood pressure and oxygen saturation	Х
Nasopharyngeal swabs x2 (simultaneously taken) for initial testing by standard Cepheid device and novel Logicore System device	Х
Additional nasopharyngeal swab for testing by second-line device*	Х
Assessment of acceptability (Likert-scale)	Х
Adverse event details	Х

^{*}Additional nasopharyngeal swab may or may not be required, depending on the results from the initial testing and depending on the clinical status of the participant according to Trust IPC policy.

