13.5.3 Study Sample Collection and Testing Process

Study staff undertaking the sample collection will wear appropriate personal protective equipment (PPE) for the risk exposure at all times, in line with CUH local guidelines for Infection Prevention and Control. To eliminate potential differences in the samples being tested, two nasopharyngeal swabs will be collected simultaneously. One swab will be tested by the gold standard Cepheid multiplex POC test (i.e. standard of care diagnostic testing as required by CUH Trust IPC policy) and the other with the novel Logicore System multiplex POC device. The Logicore System swab will be tested using a specific Logicore System buffer which will be provided for use in a closed vial by the Sponsor. The testing of each specimen (Cepheid or Logicore) must begin within 20 minutes from the time of swab collection, according to the specimen processing guidelines. There is no need to store the swabs/buffer solutions on ice. These can remain at ambient temperature for storage.

The Cepheid POCT is done in the laboratories above the ED. The Logicore System (i.e. the Analytical Module into which the Respiratory Pathogen Panel cartridge is loaded for analysis and the portable Operation Module with display screen, into which the cartridge details and participant anonymised details are input) will be located in a secure clinical area within the ED, with controlled access.

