14.6 Estimand Table

Objective	Treatment / Strategy	Population	Variable (Outcome)	Intercurrent Events	Summary Measure (Estimand)
Primary: Compare diagnostic sensitivity and accuracy of new POCT vs gold standard for 4 respiratory infections	New POCT vs v gold standard POCT	symptoms meeting	Diagnostic test result (positive/negative) per pathogen	- Invalid swab or test - Withdrawal before testing - Gold standard indeterminate	Difference in sensitivity and specificity; 95% CIs for each; McNemar's test for paired comparisons
Secondary 1: Compare turnaround time from swab to result	New POCT vs gold standard POCT	Same as above	Time (minutes) from sample collection to result availability	- Missing timestamps Result delayed due to user error or system failure	- Mean/median time per method; Paired t-test or Wilcoxon signed-rank test
Secondary 2: Compare specificity of new POCT vs gold standard	Same as above	Same as above	Diagnostic result per pathogen in gold standard negative patients	- Invalid test - Patient lost to follow-up	Specificity per infection type; 95% CI
Secondary 3 & 4: Estimate PPV and NPV of new POCT	New POCT	Same as above	PPV = TP/(TP+FP); NPV = TN/(TN+FN)	- Inconclusive reference test result	PPV, NPV per infection; descriptive analysis with 95% CI
Secondary 5: Assess patient acceptability of new test	New POCT	Patients providing questionnaire data	Self-reported scores on comfort, experience, willingness to retest	- Non-response - Incomplete questionnaire	Median scores; frequencies; thematic analysis for free text

CONFIDENTIAL

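### The planned Wilcoxon signed-rank comparison of participant acceptability has no standard-test rating to pair with, and the answers collected describe a double swab rather than the Logicore swab.

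*Protocol*

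**What the plan says.** **Planned analysis.** Protocol 14.5.3 says: "Participants will complete a brief questionnaire assessing the acceptability of the new POCT including comfort and willingness to repeat the test". It then adds that "comparisons with the standard test will be conducted using Wilcoxon's signed-Rank test using JASP software". Sections 14.2.3 and 14.3.3 plan the same comparison.

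**Data collected.** Section 11 sets out two participant items. The first, "How unpleasant was the swab", has four ordered categories. The second, "If you had to have the swab done again, how would you feel about it", has three. Section 11 reads the first item's score as a measure of how acceptable the swabbing process was. A separate item asks research staff how hard the Logicore System was to use.

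**Sampling.** The schedule in 13.5.1 lists "Nasopharyngeal swabs x2 (simultaneously taken) for initial testing by standard Cepheid device and novel Logicore System device" and a single acceptability assessment at the one visit. Section 13.5.3 confirms that "two nasopharyngeal swabs will be collected simultaneously", and the synopsis specifies one per nostril.

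**Estimand.** The acceptability row in 14.6 names the new test as the only strategy. Its summary measures are medians, frequencies and "thematic analysis for free text". It has no comparator and no test.

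**The concern.** The signed-rank test works on within-person differences. It needs a Logicore score and a Cepheid score from the same participant, and the protocol appears to collect only one score per item. If so, a stated analysis of a secondary endpoint has no data.

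There is also a question of interpretation. With both nostrils swabbed together and one answer given, the answer belongs to the pair of swabs. If it were reported as acceptability of the new test, it would credit or blame Logicore for an experience that is half routine care. The participant also has little contact with either device. Under 13.5.3, Cepheid runs in laboratories above the department and Logicore in a controlled-access area.

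The gap lies in data collection, which the protocol fixes. A separate SAP could drop the comparison, but it could not supply a rating that was never asked for.

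**Working it through.** The acceptability sections state no sample size, effect size or power, so there is no figure to reproduce. The check sets what the test needs beside what is collected.

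**Step 1: what the test needs.** For participant *i* and a given item, the signed-rank test uses d_i = (score for Logicore) − (score for Cepheid). Both terms must be observed.

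**Step 2: what is collected.**

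| Source | Content | Cepheid rating? |
|---|---|---|
| Section 11, item 1 | One four-category answer; swab in the singular; no device named | No |
| Section 11, item 2 | One three-category answer; no device named | No |
| Section 11, staff item | Logicore only | No |
| 13.5.1 schedule | One acceptability assessment at the visit | No |
| 14.6 acceptability row | New test alone; medians and frequencies | No |

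**Step 3: count.**
- Answers collected: up to 400 participants × 2 items × 1 answer = 800.
- Answers needed for a paired comparison on both items: 400 × 2 items × 2 tests = 1,600.
- Within-person differences d_i available on either item: 0 of 400.

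A one-sample signed-rank test against a fixed value could be computed from the 400 single answers per item. It would not compare anything with the standard test.

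**Step 4: can the single answer stand for Logicore?** No. The two swabs are simultaneous, the item does not say which one is meant, and section 11 itself describes the first item's score as reflecting the swabbing process. Section 15.6 adds that discomfort and bleeding are expected to be the same as with the standard procedure. The answer therefore measures the dual-swab procedure.

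**Step 5: internal consistency.** Sections 14.2.3, 14.3.3 and 14.5.3 promise a paired comparison, while the 14.6 row is descriptive and concerns one test only. They cannot both describe the analysis. The 14.6 row also promises a thematic analysis of free text, although both participant items in section 11 are closed. Its list of self-reported scores includes experience, which matches neither item clearly.

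**The case against.** The strongest defence is that the endpoint itself is not comparative. Sections 9.2 and 10.2 and the synopsis ask only for an evaluation of Logicore's acceptability to participants and staff. The estimand row agrees, whereas turnaround time is expressly a comparison. On this view the error is one clause repeated in three analysis paragraphs. With no paired data, it cannot even yield a misleading p-value. This stands as a limit on the point's reach. It does not rescue the clause, and it leaves open the attribution of a double-swab rating to Logicore.

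A reader might infer four stronger points that the documents do not support:

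- **That secondary endpoint 2 fails as a whole.** It does not. It makes no comparative claim, descriptive reporting remains possible, and the staff part asks about Logicore by name.
- **That the two items are miscoded because their scales run in opposite directions.** Section 11 applies its higher-is-better rule to the first item, before the second is introduced. No composite is planned, and separately reported items need no common direction.
- **That the free-text analysis must be deleted.** The questionnaire form is not in the document and may hold more than the two quoted items. The text supports reconciling the two places, not deletion.
- **That the staff item can simply carry device acceptability instead.** Sections 14.2.3, 14.3.3 and 14.5.3 describe no staff analysis, and the 14.6 row is limited to patients. Section 11 lists the staff assessment among the data collected at each visit, so the same staff may rate repeatedly.

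**Conclusion.** The point holds. The paired comparison of participant acceptability with the standard test cannot be run on the data the protocol collects: 0 of up to 400 participants will have a pair of scores. The comparison also contradicts the estimand row. The answers that will exist describe the dual-swab procedure and cannot be attributed to the Logicore swab.

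This rests on section 11 giving the participant items in full as regards a per-device rating. Nothing in the protocol suggests that a separate Cepheid rating is asked for elsewhere.

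The consequence is moderate. A named secondary endpoint has an analysis that must be abandoned or misdescribed, but it has no success criterion and does not drive the sample size. The primary accuracy results are untouched. It should be corrected before recruitment, because an unasked rating cannot be recovered reliably afterwards.

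**What to change.** Choose one of two routes before the first participant is enrolled.

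**Route A: drop the comparison.** Delete the clause on comparison with the standard test from 14.2.3, 14.3.3 and 14.5.3. Report each participant item descriptively as acceptability of the dual-swab procedure. Align the wording of the acceptability objective and endpoint (synopsis, 9.2, 10.2) and of the 14.6 row. The cost is textual edits in several sections and a narrower participant claim.

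**Route B: collect the missing rating.** Ask each item separately for each swab and record which device each nostril's swab went to, preferably with that allocation randomised. Section 11 and the schedule in 13.5.1 would change. If allocation is randomised, the statements that there is no randomisation would need a qualifying line. The signed-rank test then has its pairs. The cost is two extra short answers per participant (2 items × 1 additional swab, up to 800 in all). It also assumes participants can tell two simultaneous swabs apart. Even then the result compares swabs, not devices, and should be reported as such.

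**Under either route,** reconcile the free-text analysis in 14.6 with the closed items in section 11: either identify the free-text field on the form or amend the row.

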14.6 Estimand Table

Objective	Treatment / Strategy	Population	Variable (Outcome)	Intercurrent Events	Summary Measure (Estimand)
Primary: Compare diagnostic sensitivity and accuracy of new POCT vs gold standard for 4 respiratory infections	New POCT vs v gold standard POCT	symptoms meeting	Diagnostic test result (positive/negative) per pathogen	- Invalid swab or test - Withdrawal before testing - Gold standard indeterminate	Difference in sensitivity and specificity; 95% CIs for each; McNemar's test for paired comparisons
Secondary 1: Compare turnaround time from swab to result	New POCT vs gold standard POCT	Same as above	Time (minutes) from sample collection to result availability	- Missing timestamps Result delayed due to user error or system failure	- Mean/median time per method; Paired t-test or Wilcoxon signed-rank test
Secondary 2: Compare specificity of new POCT vs gold standard	Same as above	Same as above	Diagnostic result per pathogen in gold standard negative patients	- Invalid test - Patient lost to follow-up	Specificity per infection type; 95% CI
Secondary 3 & 4: Estimate PPV and NPV of new POCT	New POCT	Same as above	PPV = TP/(TP+FP); NPV = TN/(TN+FN)	- Inconclusive reference test result	PPV, NPV per infection; descriptive analysis with 95% CI
Secondary 5: Assess patient acceptability of new test	New POCT	Patients providing questionnaire data	Self-reported scores on comfort, experience, willingness to retest	- Non-response - Incomplete questionnaire	Median scores; frequencies; thematic analysis for free text

CONFIDENTIAL

15.0 ADVERSE EVENTS AND REPORTING

15.1 Definition of an Adverse Event

As per MHRA Clinical Trials Guidance⁸, an Adverse Event (AE) is any untoward medical occurrence, unintended disease or any untoward clinical sign in a clinical investigational subject, temporally associated with the subject's participation in research, whether or not it is considered related to the study procedures, investigational medical device or comparator.

15.2 Definition of a Serious Adverse Event (SAE)

A Serious Adverse Event (SAE) is any untoward medical occurrence that results in any of the following:

- 1) Death
- 2) Life-threatening illness or injury (at the time of event; not which hypothetically might have caused death if it were more severe)
- 3) In-patient hospitalisation or prolongation of existing hospitalisation
- 4) Permanent impairment of a body structure or body function
- 5) Congenital abnormality or birth defect
- 6) Any other important medical event, considered to be serious by the Investigator.

15.3 Definition of an Adverse Device Effect (ADE)

An Adverse Device Effect (ADE) is an Adverse Event (AE) related to use of an investigational medical device (including an IVDD). This includes any AE resulting from insufficiencies or inadequacies in the instructions for the use, deployment, operation or any malfunction of the investigational medical device. This includes any AE that is a result of a user error or intentional misuse of the device.

15.4 Definition of a Serious Adverse Device Effect (SADE)

A Serious Adverse Device Effect (SADE) is an adverse device effect that results in any of the following:

1) Death

- 2) Life-threatening illness or injury (at the time of event; not which hypothetically might have caused death if it were more severe)
- 3) In-patient hospitalisation or prolongation of existing hospitalisation
- 4) Permanent impairment of a body structure or body function
- 5) Congenital abnormality or birth defect
- 6) Any other adverse device effect considered to be serious by the Investigator.

As the Logicore POCT device study does not involve an Investigational Medicinal Product, non-serious Adverse Events will not be collected in the study Case Reporting Form (CRF). Only those Serious Adverse Events and Serious Adverse Device Effects (SAEs and SADEs) as defined above, that are suspected to be specifically related to the study procedures or the study device, in the opinion of the Investigator, will be collected in the CRF and reported accordingly.

It is recognised that there may be many deaths in hospital due to infection caused by respiratory pathogens, but the death of a participant in this study would only be relevant if it was deemed due to the procedures or investigative device used for the study. This pragmatic approach to the proportionate reporting of SAEs and SADEs is in line with the updated 'ICH Guideline for Good Clinical Practice E6 (R3)'9 which has already been implemented in the EU, and which will be adopted in the UK in 2026.

